Cancer is the leading cause of death among Asian Americans, and mortality from colorectal cancer is ranked as the second most common in cancer deaths among Asian Americans. However, recent data show that colorectal cancer screening rates are substantially lower for Chinese and Korean Americans compared with other racial/ethnic groups. To date, a small number of community-based studies have reported on the use of single level (participant level only) interventions to increase colorectal cancer screening rates among Chinese and Korean Americans; however, very little is known about the impact of multi-level (patient-oriented and provider-oriented) interventions on colorectal cancer screening adherence among Chinese and Korean American patients in primary care setting. Furthermore, our preliminary data indicate physician's recommendation as the strongest facilitator of colorectal cancer screening among Chinese and Korean Americans. Thus, the primary objective of the study is to address this important knowledge gap by conducting a randomized controlled trial to determine the impact of a multi-level culturally-sensitive decision support intervention on colorectal cancer screening adherence among 400 Chinese and Korean American primary care patients. Previous studies found that facilitating patient decision-making through decision support and providing patient navigation can increase colorectal cancer screening among diverse primary care patients.

Public Health Relevance

Cancer is the leading cause of death among Asian Americans, but colorectal cancer screening rate remains low in this population. The goal of this study is to increase colorectal cancer screening among underserved Chinese and Korean Americans through cultural adaptation and implementation of a decision support navigation trial provided in primary care setting. With growing need for linguistically and culturally competent care, more decision support, language facilitation, and navigation efforts may come into care settings; therefore, having tested interventions ready for the target population will be timely, and medical systems may benefit from having multilevel best practices known and tested for Chinese and Korean Americans.

Study Aim

The aim of the study is to determine the impact of a multi-level culturally-sensitive intervention on colorectal cancer screening adherence among 400 Chinese and Korean American primary care patients. The specific aims are to:

- (1) Implement a randomized controlled trial among 400 Chinese and Korean American primary care patients to compare colorectal cancer screening outcomes between the culturally-adjusted decision support navigation intervention and advanced control;
- (2) Determine overall colorectal cancer screening adherence and change in colorectal cancer screening decision stage in the culturally adapted decision support navigation intervention versus advanced control; and
- (3) Evaluate intervention reach, effectiveness, adoption, implementation, and maintenance.

Study Design

This study employed a cluster randomized control trial intervention study design. Participants were assigned to either the advanced control group or culturally adapted decision support navigation intervention group

Study Population

Enrollment

Twenty Chinese and Korean primary care physicians will participate in the study. Twenty Chinese and Korean American participants will be recruited from each participating primary care physicians' clinics in Maryland and Northern Virginia (in total, 400 Chinese and Korean American patients will participate in the study).

Inclusion Criteria

Eligible participants met the following inclusion criteria: male and female Chinese and Korean American patients aged 50 to 75, who are not up to date for colorectal cancer screening.

Exclusion Criteria

Those with a family history, previous history of removing polyps, inflammatory bowel disease, or diagnosis of colorectal cancer.

Procedures

- (1) Ten primary care physician clinics will be randomized to advanced control and other 10 primary care physician clinics will be randomized to the culturally adapted decision support navigation intervention. Accordingly, 200 Chinese and Korean Americans (20 participants from 10 primary care physician clinics) will be randomized to the advanced control and other 200 Chinese and Korean Americans (20 participants from 10 primary care physician clinics) will be randomized to the culturally adapted decision support navigation intervention. In total, 400 Chinese and Korean Americans will participate in this project.
- (2) All 400 participants will be invited to primary care physician's clinic or community organization, where the participant will provide informed consent and HIPAA authorization form and complete a baseline survey (see sample). Participants' height, weight and waist/hip circumference, blood pressure, blood glucose and cholesterol levels will be measured by trained research staff.
- (3) Those randomized to the advanced control group will receive informational booklet regarding colorectal cancer and colorectal cancer screening, colonoscopy instructions, stool blood test kit and a result of body measurements as a free service. They will receive a reminder by mail after 45 days of random assignment.
- (4) Those randomized to the culturally adapted decision support navigation intervention group will receive everything the advanced control receives, and will receive a phone call from a patient navigator. The patient navigator will verify the participant's preferred colorectal cancer screening test. During this encounter, the patient navigator will also use a theory-based online Decision Counseling Program© to identify barriers to and facilitators of preferred test performance, determine the likelihood of test performance, and develop a personal screening plan. The counseling call will take about 45 minutes. The patient navigator will print out this screening plan and share it with the participant and primary care physician's office. After 45 days of random assignment, those in the culturally adapted decision support navigation intervention group will receive a reminder by mail.
- (5) Six months after randomization, trained and blinded bilingual survey interviewers will contact each participant by telephone and administer a 6-month Survey. This will take about 20 minutes. Six-month medical record review will be also completed by the survey interviewer.
- (6) The patient navigator will create a colorectal cancer screening status report for participants in the culturally adapted decision support navigation intervention, and share it with the primary care physician and office manager. The report will indicate whether the participant adhered to the screening, and if the participant needs diagnostic follow-up for an abnormal stool blood test result.
- (7) At 12 months after randomization, an endpoint medical record review will be performed on all study participants to assess colorectal cancer screening adherence. Self-reported colorectal cancer screening data will be collected by phone. Survey interviewer will ask participants if they had colorectal cancer screening in past 6 months.

Outcomes

Participants will complete a pen and pencil questionnaire at baseline. At 6-month follow-up, participants will participate in phone survey and their medical records will be reviewed. At 12-months after randomization, the medical records of all participants will be reviewed by research team staff. Phone follow-up will be conducted to collect self-reported data on colorectal cancer screening. Previously validated measures to assess belief, attitude, cohesion, self-resilience and knowledge about

colorectal cancer screening and colorectal cancer, health literacy, religion, social support, acculturation and colorectal cancer screening adherence will be used in baseline and 6-month surveys.

Primary Outcome Measure:

- **Colorectal Cancer Screening Adherence**
 - Description: measure to assess colorectal cancer adherence among participants
 - Time Frame: at 6-month and at 12-month
- **Overall colorectal cancer screening adherence by self-report and medical record review**
 - Description: measure overall colorectal cancer screening adherence by self-report and medical record review
 - Time Frame: at 6 months and at 12 months
- **Colorectal cancer screening decision stage for stool blood test and colonoscopy**
 - Description: measure colorectal cancer screening decision stage for stool blood test at baseline and 6 month
 - Time Frame: Baseline and 6-month
- **Change in colorectal cancer screening decision stage for stool blood test and colonoscopy**
 - Description: measure change in colorectal cancer screening decision stage for stool blood test and colonoscopy
 - Time Frame: 6 months
- **Colorectal cancer screening test-specific adherence for stool blood test and colonoscopy**
 - Description: measure the fraction of participants who undergo a stool blood test and colonoscopy
 - Time Frame: at 6 months and at 12 months

Ethical Considerations

This study was reviewed and approved by the University of Maryland, College Park Institutional Review Board. Prior to participation in the study, participants will provide informed consent.

Potential Risks and Discomforts

There are minimal risks to participants involved in this study. It is possible that thinking about cancer could cause stress or anxiety for some participants. Some participants may feel uncomfortable when the research team conducts body measurement. These are routine procedures that participants usually go through in their check-up; however, if they feel uncomfortable, participants can choose not to participate in it. Although somewhat likely, these risks are not considered serious because the questionnaires and body measurement assess only minimally sensitive issues and they pose little risk. Lastly, loss of confidentiality is always a risk with human participants; however we consider this risk minimal and have adopted multiple safeguards to ensure that confidentiality is protected.

Benefits

We believe there are benefits associated with learning about cancer screening and other health promotion behaviors. The intervention may increase the salience or awareness of the importance of these behaviors to participants. We also believe that learning about one's body measurements will help them to maintain healthy lifestyle. Furthermore, the study may work as a reminder for participating primary care physicians to recommend colorectal cancer screening to their other patients who are not participating in the study.

Confidentiality

Confidentiality will be assured in the following way. Participants will be assigned a four-digit participant identification number, at the time of enrollment. Participant identifiers will be stored electronically in password-protected databases and in hard copies stored in locked file cabinets. In order to reduce the risk of loss of confidentiality, access to personal identification information will be limited to the study's Principal Investigator ([name]) and the research staff. We have used these methods in past research and they have been extremely effective in protecting against potential risks. All research records will be kept for 10 years. After 10 years, all electronic records will be deleted from computer and all hard copies of data will be shredded.

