STOP CRC Program (NIH R01) Statistical Analysis Plan

Official Trial Title: Culturally Adapted Multilevel Decision Support Navigation Trial To Reduce Colorectal Cancer Disparity Among At-Risk Asian American Primary Care Patients

Unique Protocol ID: R01MD012778

Document Date: 3/1/2018

Lead Organization: University of Maryland

Participating Site Information: University of Maryland School of Public Health

NCT Number: NCT03481296

CONTACT INFORMATION:

[name], Principal Investigator
[name]
Department of Epidemiology and Biostatistics
University of Maryland School of Public Health
[name] 20742-2611
[contact]
[contact]

[name], MS, Central Contact
[name]
Department of Epidemiology and Biostatistics
University of Maryland School of Public Health
[name]
[contact]
[contact]

Statistical Analysis Plan

Determine overall screening adherence in the culturally adapted decision support navigation intervention vs. the advanced control. The two study groups will be compared in terms of the fraction of participants who undergo colorectal cancer screening (through stool blood test or colonoscopy) within 12 months of the randomization date. Screening status will be determined using the 6-month survey, 12-month self-report of screening, and medical record review data at 6 and 12 months. We hypothesize that participants in the culturally adapted decision support navigation intervention group will have higher overall colorectal cancer screening rate than participants in the advanced control group. Generalized Estimating Equation (GEE) models with a logit link will be used to adjust for nesting of participants within primary care physicians. Specifically, the dependent variable is the screening status (yes vs. no) and the main predictor is the intervention groups (culturally adapted decision support navigation intervention versus advanced control). As mentioned above, we expect the two study groups to be comparable at baseline due to randomization. So, the model will control only for participant gender, age, and ethnicity (Chinese or Korean) (these three variables will be included to allow addition of interaction between study group and gender, age, or ethnicity in secondary analyses). If, however, substantial baseline imbalances occur, the model will control for additional variables.

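### The endpoint chart review falls at 12 months, the same day the 12-month endpoint window closes, so tests from the last weeks may not yet be on file

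*Protocol*

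**What the plan says.** **Endpoint window.** The SAP's paragraph on overall screening adherence compares the arms on the fraction having either test "within 12 months of the randomization date".

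**Chart review.** Protocol, Procedures, step (7): "At 12 months after randomization, an endpoint medical record review will be performed on all study participants to assess colorectal cancer screening adherence". Neither document describes a waiting period before this review or a further look at the charts after it.

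**Phone call.** The same step adds self-report: "Survey interviewer will ask participants if they had colorectal cancer screening in past 6 months".

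**Combining sources.** The SAP states: "Screening status will be determined using the 6-month survey, 12-month self-report of screening, and medical record review data at 6 and 12 months". It gives no rule for a participant who reports a test that the chart does not show.

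**Outcomes.** Under Primary Outcome Measure, the protocol lists adherence with no source named, overall adherence by self-report and record review, and adherence to each test separately, all at 6 and 12 months.

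**Status report.** Procedures, step (6), provides a report for intervention participants only, which goes to the physician and office manager: "The report will indicate whether the participant adhered to the screening". The step carries no date. It stands between the 6-month and 12-month steps.

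**The concern.** A test counts by the date it was done, but a chart shows it only once the result has been filed. When the review coincides with the end of the window, a test from the last weeks can meet the SAP definition and still be unseen. This matters most for a colonoscopy done outside the primary care office, although the documents do not say where colonoscopies are done or how quickly results arrive. Nothing later corrects the omission.

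Self-report covers the same weeks, so what remains exposed is narrower:

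- participants whom the 12-month call does not reach, or who misreport;
- the test-specific outcome, because the call is described only as asking whether screening took place, so the chart is the only described 12-month source for which test was done and when;
- any result in which the chart must confirm a self-report or overrides it, which the documents neither require nor exclude.

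At stake is a small understatement of the 12-month rates and, if late tests are more frequent in one arm, a small distortion of the difference between arms.

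**Working it through.** **The plan's own figure.** 20 clinics × 20 patients = 400, and 10 × 20 = 200 per arm. This reproduces. In an arm of 200, one percentage point is 2 patients. The documents give no expected screening rates, filing lag or phone contact rate, so the size of the loss cannot be derived from them.

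**Assumed inputs (none from the documents).**

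- h: share of an arm whose first test falls in months 6 to 12, spread evenly over 365/2 = 182.5 days.
- L: filing lag, 30 to 60 days, applied to every test.
- u: share of late tests not recovered by self-report. u = 1 for records alone; u = 0.20 if 20% are not reached, those reached report correctly, and a positive self-report counts. Participants not reached and without a chart entry are taken as not screened; the documents give no missing-data rule.

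**Formula.** Points missed in an arm = h × (L / 182.5) × u. The change in the difference is control points missed minus intervention points missed.

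Example, L = 60, records alone: 15% × 60/182.5 = 4.9 and 5% × 60/182.5 = 1.6, so the difference shrinks by 3.3 points. Multiplying by 0.20 gives 0.99 and 0.33, a shrinkage of 0.7.

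| h, intervention / control | L (days) | Missed, records alone | Change in difference | Missed, with self-report | Change in difference |
|---|---|---|---|---|---|
| 15% / 5% | 30 | 2.5 / 0.8 | −1.6 | 0.49 / 0.16 | −0.3 |
| 15% / 5% | 60 | 4.9 / 1.6 | −3.3 | 0.99 / 0.33 | −0.7 |
| 10% / 10% | 30 | 1.6 / 1.6 | 0 | 0.33 / 0.33 | 0 |
| 10% / 10% | 60 | 3.3 / 3.3 | 0 | 0.66 / 0.66 | 0 |
| 5% / 10% | 30 | 0.8 / 1.6 | +0.8 | 0.16 / 0.33 | +0.2 |
| 5% / 10% | 60 | 1.6 / 3.3 | +1.6 | 0.33 / 0.66 | +0.3 |

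**Check with other inputs.** Take h = 20% / 10% and a 4-week lag over 26 weeks. Records alone miss 200 × 0.20 × 4/26 = 6.2 tests in the intervention arm and 200 × 0.10 × 4/26 = 3.1 in control, so the difference shrinks by (6.2 − 3.1)/200 = 1.5 points. If self-report recovers 70% to 90% of these tests, the shrinkage is 0.5 to 0.15 points. Over lags of 2 to 8 weeks it is 0.8 to 3.1 points on records alone and 0.1 to 0.9 with self-report. An extreme split of 25% / 5% with an 8-week lag gives 6.2 points on records alone and 0.6 to 1.9 with self-report.

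The loss within each arm is present in every row. The sign of its effect on the difference depends wholly on the assumed split of late tests.

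**The case against.** The strongest reply is that the plan already has a second source for exactly these weeks. The 12-month call asks about the previous six months, and the SAP names that self-report as an input to screening status. A late test is then lost only if the participant is missed or misreports, or if the chart has to confirm. On the 15% / 5% inputs with self-report, the effect on the difference is at most 0.7 points, about 1 patient in 200. The SAP specifies no records-only analysis. The calculation also gives stool tests the full lag, although the reason for expecting a lag applies mainly to colonoscopy and all participants receive a stool kit.

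This stands as to size. It does not remove the point: the call cannot help those it does not reach, the question as described yields no test type or date, and nothing says that an unconfirmed self-report counts.

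A reader might infer more: that the status report prompts the intervention arm in the second half-year, so that late tests are lost mainly there and the difference is biased toward zero. The documents do not support this. The report is undated, its second-half timing is inferred only from the order of the steps, it goes to the clinic, and no contact with the participant is described. The mailed reminder at 45 days is the same in both arms. The navigator call, listed before that reminder, could instead bring screening forward and leave fewer late first tests in the intervention arm, which would reverse the sign.

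**Conclusion.** The point holds as a minor weakness in outcome ascertainment. The endpoint window and the final chart review both close at 12 months with no allowance for late filing, so 12-month rates in both arms may be slightly understated. Test-specific adherence is the more exposed outcome.

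On the assumed inputs, the difference between arms shrinks by about 0.3 to 0.7 points with self-report and 20% not reached, or by 1.6 to 3.3 points on records alone, if late tests run at 15% versus 5%. It is unchanged if late rates are equal and slightly inflated if they are higher in control. The plausible range therefore includes zero, and the documents support neither a claim that late tests are simply missed nor a claim of bias in a known direction.

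**What to change.** Keep the 12-month call where it is. Do the endpoint chart review at a fixed lag after month 12, for example 60 days, in both arms, and count only tests with a service date on or before 12 months. The endpoint itself does not change. The 60 days is an illustration; the investigators should set the lag from how long reports take to reach these clinics.

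Add one sentence to the SAP stating whether a self-reported test not found in the chart counts as screened. If it does, the call should also ask which test was done and when, so that the same cut-off and the test-specific outcome can be applied.

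Cost: revised protocol and SAP wording, possibly one longer interview question, and a final chart review and data lock about two months later. No additional chart review or participant contact is needed.

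### The 12-month call, as described, looks back only 6 months, so a participant who missed the 6-month survey gives no self-report for months 0-6 of the 12-month endpoint (minor)

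*Protocol*

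**What the plan says.** The SAP's analysis of overall screening adherence compares the arms on "the fraction of participants who undergo colorectal cancer screening (through stool blood test or colonoscopy) within 12 months of the randomization date". It names four sources: "Screening status will be determined using the 6-month survey, 12-month self-report of screening, and medical record review data at 6 and 12 months". Self-report is also part of a listed primary outcome in the Protocol, which is to "measure overall colorectal cancer screening adherence by self-report and medical record review", at 6 and 12 months.

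Protocol Procedures (5) describes the first self-report: "Six months after randomization, trained and blinded bilingual survey interviewers will contact each participant by telephone and administer a 6-month Survey". The Outcomes section lists screening adherence among the measures in that survey. Procedures (7) describes the second: "Survey interviewer will ask participants if they had colorectal cancer screening in past 6 months". It also plans a record review at 12 months: "an endpoint medical record review will be performed on all study participants to assess colorectal cancer screening adherence". The Outcomes section mentions the 12-month call again but gives no longer look-back. Neither document describes a catch-up question for someone who missed the 6-month survey, or says how a missing self-report is handled.

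**The concern.** The endpoint window is 12 months and the look-back of the last call is 6. The two self-reports join up only if both take place. Take a participant who had a stool blood test or colonoscopy in month 2, was not reached at 6 months and is reached at 12. Asked about the past 6 months, this person truthfully answers no. If the test is not in the reviewed record, a screened participant is counted as unscreened, although the person was on the phone and could have reported it.

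The unasked months matter. Procedures (3) and (4) place the mailed reminder 45 days after assignment in both arms, so the dated prompt to be screened falls in months 0-6.

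**Working it through.** **Coverage check.** The documents state no figure on this point to reproduce, so I compared the self-report windows with the SAP's 0-12 month window. I assume that the adherence item in the 6-month survey covers the time since randomization; its look-back is not stated.

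| Contacts completed | Months covered by self-report | Months resting on records alone |
|---|---|---|
| 6-month survey and 12-month call, on time | 0-6 and 6-12 | none |
| 6-month survey only | 0-6 | 6-12 |
| 12-month call only | about 6-12 | about 0-6 |
| neither | none | 0-12 |

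Only the third row can be repaired by rewording the question: the person is reached but not asked about half of the window. The repair takes self-report coverage from about 6 of 12 months to 12 of 12.

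**Illustrative size.** Every rate below is an assumption, because the documents give none. Let m be the share who miss the 6-month survey but are reached at 12 months, s the share of these screened in months 0-6, and u the share of those screenings absent from the record. The share wrongly counted as unscreened is then m × s × u.

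- Set A: 10%-25% miss the survey and half of them are reached, so m = 5%-12.5%; s = 40%-50%; u = 15%-40%. Low: 0.05 × 0.40 × 0.15 = 0.003. High: 0.125 × 0.50 × 0.40 = 0.025. That is 0.3 to 2.5 points, or 1.2 to 10 of 400 participants.
- Set B: m = 10%-30%; s = 20%-50%; u = 10%-40%. Low: 0.10 × 0.20 × 0.10 = 0.002. High: 0.30 × 0.50 × 0.40 = 0.060. That is 0.2 to 6.0 points, or 0.4 to 12 of 200 in an arm.

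Two equally arbitrary sets have upper ends more than twofold apart, so neither is an estimate. The formula also overstates the loss somewhat: it ignores people who are screened again in months 6-12 and counted then, and it assumes that every missed test would be recalled.

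**Direction.** It can go either way.

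- If m and u are equal in both arms, a true difference in months 0-6 screening shrinks by the factor 1 − m × u. Under set A, m × u runs from 0.05 × 0.15 = 0.0075 to 0.125 × 0.40 = 0.05, so the difference loses 0.75% to 5% of itself.
- Charting may instead differ by arm. Under Procedures (6), the navigator's status report goes to the physician's office for the intervention arm only. With m = 8.75% and s = 45% in both arms, and u = 15% in the intervention arm against 40% in control, the losses are 0.0875 × 0.45 × 0.15 = 0.006 and 0.0875 × 0.45 × 0.40 = 0.016. That is about 1 point in favour of the intervention.

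**The case against.** The strongest reply is that the schedule is sound as planned: two 6-month look-backs cover 12 months, shorter recall is a legitimate choice, and the gap opens only when a contact is missed. That is right for participants who complete the 6-month survey on time. It does not answer the case of someone who is reached at 12 months and is then asked a question that cannot elicit the screening.

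The second reply is that records back up self-report. The 12-month review covers all participants, does not depend on reaching them by phone and has no stated look-back limit, and a 6-month review is also planned. This stands and is the main reason why the point is minor. Still, the plan uses self-report as well as records, so it does not treat records as sufficient.

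Third, Procedures (7) is a one-sentence summary, and the script may ask more. That also stands. If it does, the sponsor need only say so.

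A reader might infer that half of the 12-month endpoint goes unmeasured, or that the result is biased toward one arm. The documents support neither. Months 0-6 are covered by the 6-month survey and by both record reviews, and no stated rate fixes a size or a direction. Late calls also shift a look-back that runs from the call date, but any fixed look-back interview has that problem.

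**Conclusion.** The point holds for one subgroup: participants without a 6-month survey who are reached at 12 months. For them, the question as described leaves months 0-6 to the records alone. A screening is lost only if the survey was missed, the test fell in months 0-6, no record review found it and no later test in the window was counted. Because all four are needed, the effect is probably small, but the documents do not allow it to be estimated. The conclusion rests on reading Procedures (7) as the whole of the 12-month question. It is a cheap improvement to the ascertainment of a primary outcome, of minor severity, and not a threat to the trial's conclusion.

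**What to change.** In Procedures (7), make the look-back depend on the last self-report. Ask a participant without a completed 6-month survey: *Since [randomization date], have you had a stool blood test or colonoscopy?* Ask all others the same question about the time since their 6-month survey, which also closes any short gap between the two contacts. Record the test type and the month and year. The catch-up should start at randomization rather than at the baseline survey, because the SAP counts from randomization and the documents do not say that the two dates coincide.

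In the SAP, count tests dated from randomization to 12 months after it. Keep a yes from the 6-month survey as it is, and keep an undated yes from a call made by month 12. An undated yes from a later call would then count only if a record places the test inside the window. The endpoint and the contact times do not change.

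The cost is one reworded phone question and a short counting rule. The downside is about 12 months' recall instead of 6, with the usual risk of misdating, but only for those who missed the 6-month survey, and it replaces no self-report at all for months 0-6. If the calls are already complete, the sponsor can instead report, by arm, how many participants had months 0-6 determined by records alone.

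### Five protocol outcomes are labelled primary without ranking, and the SAP analyses two and calls neither primary; name 12-month screening by either test as the single primary outcome and align the lists

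*Protocol*

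**What the plan says.** **Protocol.** The introductory text gives the primary objective as a trial "to determine the impact of a multi-level culturally-sensitive decision support intervention on colorectal cancer screening adherence", with no time point. Specific aim 2 joins two constructs without ranking them: "Determine overall colorectal cancer screening adherence and change in colorectal cancer screening decision stage". Under Outcomes, the Primary Outcome Measure list has five entries, and no secondary list follows:

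1. Colorectal cancer screening adherence, at 6 and 12 months.
2. "Overall colorectal cancer screening adherence by self-report and medical record review", at 6 and 12 months.
3. Decision stage, at baseline and 6 months. The title names both tests, but the text beneath covers only one: "Description: measure colorectal cancer screening decision stage for stool blood test at baseline and 6 month".
4. "Change in colorectal cancer screening decision stage for stool blood test and colonoscopy", at 6 months.
5. "Colorectal cancer screening test-specific adherence for stool blood test and colonoscopy", at 6 and 12 months.

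Item (7) under Procedures describes the 12-month record review as the endpoint review for adherence.

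**SAP.** The first analysis compares the fraction of participants who "undergo colorectal cancer screening (through stool blood test or colonoscopy) within 12 months of the randomization date", using a GEE model with a logit link and a directional hypothesis. The second compares forward movement in decision stage between baseline and 6 months, as yes or no. Neither is called primary. The SAP mentions secondary analyses only for interaction terms.

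**The concern.** A primary label tells the reader which result the trial stands on. Here it covers five entries, while the SAP analyses two constructs and gives neither the label. Two problems follow.

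First, there is more than one route to a result that the protocol's own wording would allow to be called primary. A nominally significant stage result carries the same label as 12-month screening. So would a 6-month or single-test result, although no analysis of either is prespecified. Neither document states a significance level, a testing order or any other error control.

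Second, the lists do not match. Some entries labelled primary have no planned between-group analysis, and the stage variable analysed in the SAP may not be the one listed in the protocol.

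**Working it through.** **Step 1. Match the two lists.**

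| Protocol primary entry | Time frame | SAP between-group analysis |
|---|---|---|
| 1. Adherence | 6 and 12 months | First analysis, at 12 months only |
| 2. Overall adherence, self-report and records | 6 and 12 months | First analysis, at 12 months only |
| 3. Decision stage | Baseline and 6 months | None for stage itself |
| 4. Change in decision stage, both tests | 6 months | Second analysis, possibly on a different stage variable |
| 5. Test-specific adherence | 6 and 12 months | None |

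That gives five entries labelled primary, two SAP analyses, and none named primary in the SAP. Entries 1 and 2 may be the same outcome. Only entry 2 names its data sources, and nothing else separates them.

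**Step 2. Compare the stage definitions.** The protocol lists stage change for stool blood test and colonoscopy. The SAP elicits a stage for each test, computes an overall stage as the higher of the two, and then defines forward change as any upward movement without saying which stage is meant. The definitions can disagree. A participant who has already decided on a stool test at baseline is at the top overall stage. If that participant newly decides on colonoscopy by 6 months, the colonoscopy stage moves forward and the overall stage cannot.

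**Step 3. Look for a figure that settles the priority.** The only sample-size figure is the total of 400: 20 clinics × 20 participants = 400, or 10 × 20 = 200 per arm. It is internally consistent. No power, effect size, event rate or significance level accompanies it, so it cannot show which outcome the trial was sized for.

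**Step 4. Error rate for the SAP's two tests.** Assumptions, none stated in the documents: each test is two-sided at 5% (critical value 1.96), success on either could be claimed as primary, and the two test statistics are jointly normal with correlation ρ when there is no effect.

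- Any false positive: 1 − P(|Z₁| < 1.96 and |Z₂| < 1.96). At ρ = 0 this is 1 − 0.95² = 0.0975.
- False positive favouring the intervention: 1 − P(Z₁ < 1.96 and Z₂ < 1.96). At ρ = 0 this is 1 − 0.975² = 0.0494.

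For ρ > 0 the bivariate normal probability is used:

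| ρ | Any false positive | Favouring the intervention |
|---|---|---|
| 0 | 0.0975 | 0.049 |
| 0.5 | 0.091 | 0.045 |
| 0.7 | 0.083 | 0.042 |
| 0.9 | 0.070 | 0.035 |
| One primary outcome | 0.050 | 0.025 |

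The upper bound for any false positive is 0.05 + 0.05 = 0.10.

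**The case against.** The strongest reply is that the main question is plain enough. The stated objective is screening adherence, the 12-month record review is described as the endpoint review, and the SAP puts 12-month screening first, with a directional hypothesis and its fullest model. This largely stands. A reader might infer from the five-entry list that nobody could tell what the trial is about, and the documents do not support that. What remains is that the objective has no time point, aim 2 joins adherence with stage change, and the only explicit label in the protocol makes stage and single-test outcomes primary too.

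A second reply is that counting outcomes exaggerates the multiplicity. This also stands. Entry 3 can be read as the measurement behind entry 4. The 6-month adherence data can be read as feeding one cumulative variable, since the SAP says "Screening status will be determined using the 6-month survey, 12-month self-report of screening, and medical record review data". A reader might multiply entries by tests and time points to reach a much larger error rate, but that would rest on a contestable count and on tests the SAP does not plan. The calculation is therefore limited to the SAP's two tests.

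Third, the 7-10% needs a rule that either result is enough, and no passage states one. If the SAP's stage change uses the overall stage, it is also not exactly the variable listed in the protocol. Both points make the figure conditional. They do not remove the labelling conflict.

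Fourth, the documents do not mandate a single primary outcome. Two primaries with a split significance level, or a fixed testing order, would also control error. That is true. One primary outcome is preferred because it fits the stated objective and leaves the main test at its full level.

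**Conclusion.** The point holds as a conflict of labelling and alignment, and should be corrected. The protocol labels five outcomes primary, and the SAP plans two analyses without ranking them. Three items under the primary label have no planned between-group analysis: 6-month adherence as a separate endpoint, test-specific adherence, and decision stage itself.

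The size is modest. The chance of at least one false positive is about 7-10% (4-5% favouring the intervention), against 5% (2.5%) with one primary outcome. This assumes two-sided 5% per test, correlation between 0 and 0.9, and that either result could be claimed as primary.

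A reader might also infer that the stage definitions would give materially different results. The documents show that they can differ for an individual participant, but they give no stage distribution from which to say how often. Nor do they establish that entries 1 and 2 are duplicates.

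**What to change.** - In both documents, name overall screening (stool blood test or colonoscopy) within 12 months of randomization as the single primary outcome.
- Make forward stage change secondary, state whether it uses the overall (higher-of-two) or the test-specific stage, and make the protocol entry match.
- Merge the first two adherence entries, or say how they differ.
- Relabel 6-month adherence, test-specific adherence and decision stage as secondary with a matching SAP analysis, or as descriptive only. The GEE model already planned would serve the binary outcomes.
- Settle the designation before outcome data by group are seen, or report it as a later decision. The Study Design section uses the past tense while Procedures uses the future, so the stage of the trial is not clear from the documents.

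The cost is revised protocol wording and some SAP text, with no new data. The downside is that a 6-month, single-test or stage result can no longer be presented as the primary finding.
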